Official Title: PRP vs PRP Plus IGF for Patellar Tendinosis

NCT Number: NCT04350827

Document date: June 2, 2020

TITLE: A comparison of two different platelet-rich plasma injections for patellar tendinosis: a randomized, double blinded comparative trial.

I. Objective:

The purpose of this study is to compare two different platelet-rich plasma (PRP) injections for patellar tendinosis.

Introduction/Background:

Patellar tendinosis is a frustrating ailment commonly encountered in sports medicine. Treating this condition continues to be a significant challenge for sports medicine physicians.^{3, 11, 13} The tendinosis lesion is characterized by collagen disorganization and increased ground substance. One method of treating this problem is using platelet rich plasma (PRP), which is a concentration of platelets from the patient's own blood that provides a high dose of growth factors aimed at stimulating tendon healing. These injections have been used extensively to treat many tendon disorders including patellar tendinosis. Several studies have demonstrated the safety and efficacy of using PRP to treat patellar tendinosis.^{1, 2, 4-6, 12, 14}

One growth factor that is known to be helpful in tendon healing is insulin-like growth factor (IGF).^{7, 9} However, IGF is not found in PRP but rather in the free plasma that is spun off during the PRP processing.⁸ This free plasma or platelet poor plasma (PPP) is typically discarded but it is a known source of IGF. We have shown that concentrating PPP in the FDA cleared Plamax device yields an increased concentration of IGF.¹⁰ Local IGF injections into the patellar tendon have demonstrated improved tendon healing, but the effect on clinical outcomes has never been studied in a controlled fashion.⁷

Aim: To perform a randomized, double blinded study comparing the clinical effect of PRP versus PRP + concentrated IGF in patients with patellar tendinosis.

III. Procedures:

A. Research Design: Double blinded randomized comparative trial.

B. Patients:

Sample: 38 total volunteers (19 per treatment arm, accounting for 15% dropout with goal of 16 per group). This is sufficient to detect a change of 13 points (the minimal clinically important difference).

Inclusion:

- >6 weeks of symptomatic patellar tendinosis
- unilateral or bilateral
- 14 yrs of age or older
- active in sport and exercise at least 3x / week
- able to take time away from sport (for healing and rehabilitation phase after procedure)
- failed at least 6 weeks of guided rehabilitation (under the supervision of either a certified athletic trainer or physical therapist)
- Minimum Tegner activity level of 4

Exclusion: Prior injection therapy:

- Steroid injection in target knee in the last 3 months
- PRP in the target knee in the last 6 months

No other cellular treatments in index knee (bone marrow, amniotic suspensions) last 1 year

Participation in any experimental device or drug study within 1 year before screening visit

Oral or IM steroids for last 3 months

Dry needling of patellar tendon in last 6 months

Medical condition that may impact outcomes of procedure including

anemia

thrombocytopenia

bleeding disorders

inflammatory disorders like rheumatoid arthritis, lupus

diabetes

any history of cancer (other than non-melanoma skin malignancies)

taking anticoagulants (aspirin, Plavix, eliquis, Xarelto, warfarin, lovenox)

Taking immunosuppressants

Previous cartilage repair procedure on the injured cartilage surface (ie, OATS, ACI, MFX)

Previous surgery at the target knee within the past 1 year

Any degree of cognitive impairment.

Symptomatic OA of either knee

Underlying medical conditions that could interfere with evaluation of the outcome

Positive pregnancy test, or lactating, or intent to become pregnant during treatment period

Gout

History of infection or current infection at the affected joint

Smoking

C. Measurements

Demographics:

Age

Sex

Race

Body mass index

MRI of affected knee (if one exists in past year; none will be order as part of study)

Outcome measures (all assessed at baseline, 1,3 and 6 months).

- 1) Victorian Institute of Sport Assessment-patellar tendon (VISA-P)
- 2) Visual analog scale-Pain with ADL and Sport (VAS-P ADL and VAS-P Sport)
- 3) Tegner activity scale
- 4) Marx scale
- 5) Blazina

Ultrasound measurements (performed at clinic visit at no additional cost) at baseline and 6 months

- 1) Tendon thickness
- 2) Modified Ohberg scale

Primary outcome: VISA-P at 6 months.

In the case of competitive athletics, we will monitor time to return to sport. We will also monitor continuously for adverse events.

Schedule of Outcome Measures

	Baseline	1 mo	3 mo	6mo
VISA-P				
VAS-P ADL				
VAS-P Sport				
Tegner				
Marx				
Blazina				
Tendon Thickness		x	x	
Modified Ohberg		x	x	

Outcomes will be completed by research assistant ([name]) who will be blinded to the treatment allocation.

D. Detailed Study Procedures: 38 patients will be randomly assigned using a computer randomization scheme (from RedCap) to a treatment arm, with 19 patients for each treatment arm. Patient will be blinded to their treatment, but treatment team will not. PRP will be prepared according to standard sterile procedures out of view of the patient to ensure patients are adequately blinded. The injecting physician ([name]) will not be blinded to randomization scheme.

PRP:

Procedure will be carried out with excellent sterile technique. 54ml of whole blood will be drawn. 54ml will be processed by centrifugation using the GPS III system (Zimmer Biomet, Warsaw, IN) and 1 ml will undergo a complete blood count (for a baseline comparison to determine the fold increase in platelets). The resultant PRP (5ml) will be injected (after 5ml 1% lidocaine has been injected into the skin for comfort) into the patellar tendon using ultrasound guidance to accurately direct the injection to the site of the tendon abnormality. The patient will rest after the injection for 15 minutes and then be dismissed.

PRP + concentrated IGF

The PRP preparation and blood draw will be identical to the above. 55ml of whole blood will be drawn (1ml will undergo a CBC and the remaining 54ml will be used to make PRP). In addition to preparing the PRP, the resultant PPP (instead of discarding it) will be placed into the Plamax device (Zimmer Biomet, Warsaw, IN) and concentrated via a second centrifugation cycle. The plamax concentrate (concentrated IGF) will be added to the PRP (3ml of PRP + 2ml of plamax concentrate for a total of 5ml) and then will be injected (after 5ml 1% lidocaine has been injected into the skin for comfort) under ultrasound guidance followed by the same rest period.

The injection volume for each group will be identical (5ml total).

For each patient, 1ml of whole blood of 1ml of PRP will be tested for a total cell count

After Care

Patients will avoid NSAIDs for the remainder of the trial. They may ice and use Tylenol.

For the 1st month, patients will be given a home rehabilitation plan consisting of range of motion and gentle strengthening.

In month 2, they will be allowed to return to sport as tolerated.

F. Data Analysis: Continuous variables will be checked for normality and subsequently compared using either unpaired t-tests (for normally distributed data) or Mann-Whitney U test (for non-normally distributed data).

Patient incentive:

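### The planned test of 6-month VISA-P leaves out patients without a 6-month score and makes no use of the baseline, 1- and 3-month scores; using them is a cheap improvement

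*Combined protocol and SAP*

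**What the plan says.** Section III.B (Sample) plans "38 total volunteers (19 per treatment arm", "accounting for 15% dropout with goal of 16 per group", and says this suffices to detect 13 points, described as the minimal clinically important difference. It gives no SD, significance level or power.

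Section III.C schedules VISA-P four times: "Outcome measures (all assessed at baseline, 1,3 and 6 months". It then fixes the endpoint: "Primary outcome: VISA-P at 6 months".

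Section III.F is one sentence: "Continuous variables will be checked for normality and subsequently compared using either unpaired t-tests", with a Mann-Whitney test if the data are not normal. Nowhere does the document name an analysis set, a rule for missing 6-month scores, a baseline covariate or a repeated-measures model.

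On conduct, Section III.D states: "Patient will be blinded to their treatment, but treatment team will not". After-care is described once, for both arms: "For the 1st month, patients will be given a home rehabilitation plan consisting of range of motion and gentle strengthening", then "In month 2, they will be allowed to return to sport as tolerated".

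**The concern.** Neither named test can use a patient who has no 6-month score, so the default primary comparison rests on about 32 of 38 patients. The plan does not say this outright; it follows from the form of the tests and the silence on missing data. Recruiting 19 to keep 16 restores the count of completers but does nothing about which patients are missing.

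Two things are at stake. First, precision: in a trial of 38, earlier scores on the same scale can sharpen the 6-month comparison at no cost in data. Second, a conditional bias: if the treatment truly works and part of the effect is visible before patients leave, one leaving rule shared by both arms (low scorers stop attending) removes more patients from the worse arm and shrinks the observed difference.

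**Working it through.** **The plan's own figures.** 16/(1 - 0.15) = 18.8, rounded up to 19, as stated. Losing 3 of 19 is 15.8% per arm, leaving 38 - 6 = 32.

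**Implied SD (assumption: 80% power, two-sided 5%).** With 16 per arm the detectable standardised effect is 1.024, so SD = 13/1.024 = 12.7. The standard error is 12.7 x sqrt(2/16) = 4.49. If the SD is larger, power of the t-test with 16 per arm falls to 66% at SD 15 and 43% at SD 20.

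**Baseline adjustment in closed form.** Residual SD = SD x sqrt(1 - r^2). At r = 0.4 the variance factor is 1 - 0.16 = 0.84, and power at SD 12.7 rises from 80% to about 86%.

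**Simulation.** There were 20,000 replicates per case, 19 per arm and 15.8% lost overall. Assumed correlations were 0.4 from baseline to each follow-up, 0.7 for months 1-3, 0.6 for months 1-6 and 0.75 for months 3-6. The mixed model had arm-by-visit and baseline-by-visit terms, unstructured covariance and Kenward-Roger degrees of freedom. Under the shared rule, a patient in either arm leaves if the score at the relevant visit plus noise of 0.5 SD falls below one fixed cut. The true 6-month difference is 13. The half-effect case has 6.5 points present at month 3, and low 3-month scorers leave.

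| Case (SD 12.7 unless shown) | t-test bias | Power %: t-test / completer ANCOVA / mixed model |
|---|---|---|
| Random loss after month 3 | 0.0 | 80.4 / 85.3 / 88.2 |
| All loss after month 1, no effect yet | 0.0 | 83.7 / 87.1 / 85.9 |
| Half the loss after month 1, half after month 3 (effect 0, 6.5, 13) | -1.0 | 80.4 / 84.5 / 87.1 |
| Half-effect case | -1.4 | 77.4 / 82.4 / 87.8 |
| Half-effect, SD 15 | -1.4 | 63.5 / 69.3 / 75.6 |
| Half-effect, SD 20 | -1.5 | 40.9 / 45.8 / 51.4 |
| Half-effect, weaker correlations (0.2; 0.5, 0.4, 0.5) | -1.0 | 76.0 / 76.4 / 81.4 |
| Half-effect, stronger correlations (0.6; 0.8, 0.7, 0.85) | -1.6 | 78.0 / 91.4 / 94.8 |
| Full 13 points by month 1, low 3-month scorers leave | -2.7 | 66.8 / 74.6 / 87.8 |
| Leaving follows the unseen 6-month score | -3.5 | 65.2 / 72.9 / 84.7 |

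In the half-effect case at SD 12.7, 4.0 patients leave the worse arm and 2.0 the better. ANCOVA on completers still carries a bias of -1.2; the mixed model carries none. When leaving follows the 6-month score, t-test bias is -3.5 to -3.7 over SD 12.7 to 20, and the mixed model's is -1.7 to -1.8.

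**No true effect.** All three methods reject 4.9% to 5.4% of the time, under random loss or a shared rule.

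**Where the gain comes from.** Baseline adjustment adds from 76.4 - 76.0 = 0.4 to 91.4 - 78.0 = 13.4 points. The earlier visits change power by a further 85.9 - 87.1 = -1.2 to 87.8 - 74.6 = 13.2 points at SD 12.7, and up to about 14 over the SD range. The baseline share of the total gain runs from 0.4/5.4 = 7% (weaker correlations) to 13.4/16.8 = 80% (stronger). With equal correlations of 0.5, SD 15 and random loss, the standard errors are 5.30 (t-test), 4.59 (ANCOVA) and 4.53 (mixed model), so there the earlier visits add little.

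**If the analysis is of change from baseline.** The SD of change is SD x sqrt(2(1 - r)). At r = 0.4 it is 12.7 x sqrt(1.2) = 13.9, larger than 12.7. In the half-effect case a change-score t-test has bias of about -0.7 and power of about 68%.

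**The case against.** The strongest reply is that the plan does what it set out to do. On the implied SD of 12.7 and random loss, the t-test on 16 per arm delivers its 80% power without bias, so the extra points are an improvement and not the repair of an error. That stands.

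Second, the bias needs a real effect, partly present before patients leave, and loss related to scores. At -1.4 points it is about 0.3 of the 4.49-point standard error. The mixed model's zero bias in that case also owes something to simulated data that are normal, with leaving dependent on an observed score. Both remarks are fair, and the bias should be quoted by scenario.

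Third, the sample-size sentence calls the 13 points a change, so a change-score analysis may be intended, which would use baseline. The stated endpoint is the 6-month score, however, and III.F mentions no change score. Even on that reading, the 1- and 3-month scores and patients without a 6-month score stay unused, and power at r = 0.4 is lower. III.F could also cover separate 1- and 3-month comparisons, but those would not inform the 6-month one.

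A reader might go further and infer inflated false positives or loss that differs by arm for treatment-related reasons. The documents do not support either. Patients are blinded and after-care is common to both arms; the unblinded treatment team neither shows nor rules out arm-specific loss. Nor does the return to sport in month 2 show when a difference between arms would appear, so none of the timing cases can be called the likely one.

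**Conclusion.** The point holds as a cheap improvement. As written, the primary test leaves out patients without a 6-month score and does not use VISA-P data that the trial collects anyway.

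The cost is mainly efficiency. Baseline adjustment is worth about 0 to 13 points of power, and the earlier visits about -1 to +14 more. No general split between the two can be stated, because it depends on correlations that the documents do not give. Bias is 0 under random loss, no true effect, or loss before any effect. It is about -1.0 to -1.6 points if a real 13-point effect is half present at month 3 and low 3-month scorers leave, and up to about -3.7 if leaving follows the unseen 6-month score, which a mixed model only halves. All of this rests on assumed SDs of 12.7 to 20 and the correlations above. It does not show that the trial's result would be invalid.

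**What to change.** In III.F, make the primary analysis a baseline-adjusted comparison of 6-month VISA-P with patients analysed as randomised. The preferred form is a repeated-measures model of the 1-, 3- and 6-month scores, with baseline as covariate and the 6-month arm difference as the primary contrast. Multiple imputation from the earlier visits followed by ANCOVA is equally acceptable. Keep the t-test or Mann-Whitney test as a sensitivity analysis, and report the number of leavers and their last VISA-P by arm.

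A simple delta analysis is optional. For scale, a 10-point shift applied to 3 of 19 in one arm moves the difference by 3/19 x 10 = 1.6 points.

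The cost is a few sentences and slightly more programming. The drawbacks are reliance on missing-at-random, a few more parameters to estimate in 38 patients, and about 1 point less power than completer ANCOVA (86% v 87%) if all loss comes before any effect.

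### Do the 1 mL mismatches in the control arm's blood and PRP volumes undermine the equal 5 mL injections?

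*Combined protocol and SAP*

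**What the plan says.** All the volumes are in Section III.D, Detailed Study Procedures.

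- **Control arm, blood** (PRP paragraph): "54ml of whole blood will be drawn. 54ml will be processed by centrifugation", and a further "1 ml will undergo a complete blood count (for a baseline comparison to determine the fold increase in platelets".
- **Control arm, injectate** (same paragraph): "The resultant PRP (5ml) will be injected".
- **PRP + concentrated IGF arm, blood**: "The PRP preparation and blood draw will be identical to the above", followed at once by "55ml of whole blood will be drawn (1ml will undergo a CBC and the remaining 54ml will be used to make PRP".
- **PRP + concentrated IGF arm, injectate**: 3 mL of PRP plus 2 mL of Plamax concentrate.
- **Both arms, volume**: "The injection volume for each group will be identical (5ml total".
- **Both arms, cell count**: for each patient, "1ml of whole blood of 1ml of PRP will be tested for a total cell count".
- **Blinding**: "Patient will be blinded to their treatment, but treatment team will not".

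The outcomes in Section III.C are VISA-P (primary, at 6 months), two pain scales, Tegner, Marx, Blazina and two ultrasound measures. Fold increase in platelets is not listed there, and the Data Analysis paragraph (III.F) does not name it.

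**The concern.** Two sums seem not to close in the control arm, each by 1 mL.

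The first is blood: the stated uses exceed the stated draw, and two draws described as identical carry different figures.

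The second is PRP. A fold increase is a ratio, so it needs a platelet count in the PRP as well as in the blood. It is therefore natural to read the second *of* in the cell-count line as *and*, so that 1 mL of PRP is used for testing. If 5 mL is everything the centrifuge yields, the control arm cannot both give up 1 mL and inject 5 mL. The other arm needs only 3 mL of PRP for its injectate and would have enough.

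A shortfall confined to one arm would matter, because the plan promises equal injection volumes and the staff preparing the injectate know the allocation. They might inject less in control patients, or skip the control PRP count and so lose the fold increase in that arm.

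**Working it through.** **Inputs, all from Section III.D.** Control blood: 54 mL drawn, 54 mL processed, 1 mL counted. Other arm: 55 mL drawn, 54 mL processed, 1 mL counted. Injectate: 5 mL PRP in control; 3 mL PRP + 2 mL concentrate in the other arm. PRP test sample: 1 mL, if the garbled line is read that way. PRP yield Y: not stated separately, so treated as an assumption and taken as equal in both arms because preparation is called identical.

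**Figures that reproduce.** Other arm, blood: 54 + 1 = 55, which equals the draw. Other arm, injectate: 3 + 2 = 5, as stated.

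**Blood, control arm.** Uses: 54 + 1 = 55 mL against 54 mL drawn. The gap is 1 mL, or 1/55 = 1.8%. If only 54 mL were drawn, 54 − 1 = 53 mL would be left to process. This mismatch does not depend on any assumption.

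**PRP, control arm.** PRP required: 5 + 1 = 6 mL. Volume left to inject = min(5, Y − 1).

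| Assumed yield Y (mL) | Left to inject, control (mL) | Shortfall against 5 mL |
|---|---|---|
| 5.0 | 4.0 | 1.0 mL (20%) |
| 5.5 | 4.5 | 0.5 mL (10%) |
| 6.0 or more | 5.0 | none |
| Any, if 5 mL is measured after sampling | 5.0 | none |

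**PRP, other arm.** PRP required: 3 + 1 = 4 mL, so every yield in the table is enough, provided 2 mL of concentrate is also available each time.

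**What the 20% figure needs.** Three readings must all hold:

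1. The *of* in the cell-count line means *and*. This is likely, given the purpose of the count.
2. The 5 mL is the whole yield before sampling. The phrase can be read that way, but it can equally give the volume injected, and the separate statement that both groups receive 5 mL favours the second reading.
3. The test sample is taken out of that 5 mL. Nothing in the text says so.

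**Link to the analysis.** III.F compares continuous variables between arms by unpaired t-test or Mann-Whitney U test. Neither the blood volume nor the platelet ratio enters the VISA-P comparison or the figure of 19 patients per arm in Section III.B.

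**The case for a change.** The strongest case for acting is that the injectate defines what is being compared, that the blood contradiction is certain, and that the PRP ambiguity, if it bites, does so in the control arm only, in up to 19 patients. The text does not mention recording the volumes obtained, tested and injected, so equality could not be checked afterwards from what the protocol describes. A few words would settle it.

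Some of this stands. The blood figures do contradict each other, the cell-count line is garbled, and a reader cannot tell where the PRP sample comes from.

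The rest does not carry. The shortfall is one reading among several, and its range of 0 to 1 mL includes zero. Nothing suggests that staff would improvise on injected volume when the section fixes it at 5 mL for both groups; a smaller test aliquot is another way to meet both statements. The arms already differ in PRP content by design (5 mL against 3 mL), so the comparison never depended on equal PRP volume. A missing platelet count would cost a descriptive measure that is neither a listed outcome nor a named analysis. No case report form is among the documents, so volume fields may already exist.

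**Conclusion.** No change to the plan follows. The blood mismatch is a clerical slip of 1 mL (54 against 55 mL, 1.8%). The two paragraphs must be reconciled when the text is next tidied, and I take no view on which figure should stand. The PRP point is a question of clarification, not a shown error: the injected control volume would be anywhere from 4 to 5 mL depending on a yield and a sampling source that the documents do not give, and the only injected volume they state is 5 mL in each arm.

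Followed as written, the plan delivers the same 5 mL injections, the same 19 patients per arm and the same VISA-P comparison at 6 months. This conclusion rests on taking the explicit statement of equal injection volumes as governing, and on platelet fold increase having no role in the listed outcomes or the analysis. It would need another look only if records showed control patients receiving less than the stated volume.

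### The primary comparison of 6-month VISA-P ignores the baseline VISA-P that the trial collects, which is likely to lose precision with about 16 completers per arm

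*Combined protocol and SAP*

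**What the plan says.** Section III.C fixes the endpoint: "Primary outcome: VISA-P at 6 months". The same section lists VISA-P first among the clinical scores: "Outcome measures (all assessed at baseline, 1,3 and 6 months". Every patient should therefore have a baseline score, plus two intermediate ones.

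Section III.B sets the size at 19 randomised per arm, "accounting for 15% dropout with goal of 16 per group", and adds: "This is sufficient to detect a change of 13 points (the minimal clinically important difference". No SD, significance level or power accompanies that statement.

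Section III.F is the whole analysis plan, in one sentence: "Continuous variables will be checked for normality and subsequently compared using either unpaired t-tests (for normally distributed data) or Mann-Whitney U test". No covariate, regression model, change score, effect estimate or confidence interval appears there or elsewhere. Section III.D describes 1:1 allocation by REDCap and names no stratification factor.

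**The concern.** The baseline score of the same instrument is the obvious candidate to predict the 6-month score. An unadjusted comparison leaves the variation it explains in the error term. In a large trial that may be tolerable; with about 16 completers per arm it can matter.

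The word *change* in the sample-size sentence might suggest a change-score analysis. The endpoint is stated as the 6-month score, however, and III.F names no change score. A change score would in any case be less efficient than ANCOVA.

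It also matters what is reported. The plan names tests only. If the normality check selects Mann-Whitney, the named output is a P value with nothing in VISA-P points to hold against 13. A trial this small is most useful if it reports an estimate and an interval, and the width of that interval is what baseline adjustment can improve.

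**Working it through.** **Inputs from the document.** 19 randomised and 16 completers per arm, 15% dropout, 13 points (III.B); VISA-P at baseline, 1, 3 and 6 months (III.C).

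**Assumptions, because the document is silent.** Two-sided 0.05; 13 points read as a between-arm difference; baseline-to-6-month correlation r of 0.3, 0.5 or 0.7, with r = 0 as the unfavourable case; SD as below; one score per patient.

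**1. The plan's own figure.** 16/0.85 = 18.8, so 19 per arm and 38 in total: the dropout step reproduces. The 16 itself can be neither reproduced nor refuted without SD and power. Solving for the SD at 80% power:
- normal approximation: 13/[√(2/16) × (1.960 + 0.842)] = 13.1;
- t-test (noncentral t, 30 df): 12.7.

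At 90% power the t-test SD is 11.0. I use 12.7 as the anchor and 15 and 18 as less favourable values.

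**2. Unadjusted t-test.** SE = SD × √(2/16). At SD 12.7 this is 4.49, and the 95% CI half-width is 2.042 × 4.49 = 9.2 points. At SD 18 the half-width is 13.0.

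**3. ANCOVA.** The variance is multiplied by (1 − r²) × (1 + 1/28). The second factor is the expected cost of estimating the slope with 32 patients; 29 df remain. For r = 0 / 0.3 / 0.5 / 0.7 the multiplier is 1.036 / 0.943 / 0.777 / 0.528. Example at r = 0.5, SD 12.7: SE = 4.49 × √0.777 = 3.96, half-width 2.045 × 3.96 = 8.1.

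| SD | Measure | Unadjusted | r = 0 | r = 0.3 | r = 0.5 | r = 0.7 |
|---|---|---|---|---|---|---|
| 12.7 | Power | 80.0% | 78.5% | 82.2% | 88.8% | 97.1% |
| 12.7 | CI half-width | 9.17 | 9.35 | 8.92 | 8.09 | 6.67 |
| 15 | Power | 66.0% | 64.4% | 68.5% | 76.7% | 90.3% |
| 15 | CI half-width | 10.83 | 11.04 | 10.53 | 9.56 | 7.88 |
| 18 | Power | 50.7% | 49.2% | 53.0% | 61.0% | 77.5% |
| 18 | CI half-width | 13.00 | 13.25 | 12.64 | 11.47 | 9.46 |

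Break-even is r = 0.19. The equivalent unadjusted sample per arm is 16/multiplier = 17.0 / 20.6 / 30.3 at r = 0.3 / 0.5 / 0.7.

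**4. Simulation check** (15,000 trials per setting, SD 12.7). Type I error was 4.8%-5.0% for both analyses, so the planned t-test is valid. The ANCOVA-to-unadjusted variance ratios were about 0.94, 0.77 and 0.52-0.53 at r = 0.3, 0.5 and 0.7, in line with the formula.

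**5. Change score instead.** With equal SDs at both times the variance multiplier is 2(1 − r) = 1.4 / 1.0 / 0.6. Power is 65.8% / 80.0% / 95.1% at SD 12.7 and 38.7% / 50.7% / 72.3% at SD 18. It is below ANCOVA throughout, and at r = 0.3 below the unadjusted test as well.

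**6. Chance baseline imbalance.** Its 95% range in the unadjusted 6-month difference, at an assumed SD of 15, is ±1.96 × r × 15 × √(2/16) = ±3.1 / ±5.2 / ±7.3 points. This is the same lost precision seen from another side, not an additional bias.

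**7. Earlier visits of dropouts.** Letting the 3 patients per arm expected to drop out contribute any 1- and 3-month scores (between-visit correlation assumed 0.7, covariance treated as known, three dropout patterns) cuts the variance further by 5.5%-8.5% at r = 0.3, 4.5%-7.1% at r = 0.5 and 2.3%-3.8% at r = 0.7.

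**The case against.** An unadjusted comparison in a randomised trial is legitimate, and the size of the gain rests on two quantities that the document does not give. Over r from 0 to 0.7 at SD 12.7, ANCOVA power runs from 78.5% to 97.1% against 80%, so the document alone does not establish even the sign of the effect. At r = 0.3 the gain is about 2 points of power and 0.3 points of half-width. If the designers had 90% power in mind (SD 11.0), the gain is from 90% to 91.5% / 95.7% / 99.4%, which is smaller than at the 80% anchor. All of this stands as a limit on size. It does not reverse the advice: the worst case costs about 1.5 points of power, while r of 0.3 to 0.7 at the SDs tabulated gains about 2 to 27 points.

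A t-test also yields a difference and a CI, so the missing interval is a reporting gap that ANCOVA alone does not cure. That is correct. Nor would either analysis readily prove a benefit above 13 points: at SD 12.7 the unadjusted estimate would have to exceed 13 + 9.2 = 22.2.

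The validity of the planned test is conditional. Bilateral cases are eligible and the unit of analysis is not stated; an unpaired test needs one score per patient. That is a separate point, but it qualifies the statement that there is no bias.

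Finally, the mixed-model gain is small and ignores the cost of estimating an unstructured covariance from 38 patients. It therefore belongs in a supporting role only.

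**Conclusion.** The point holds. The plan's only analysis of the primary endpoint is unadjusted, although the baseline score is collected. The test is valid with one score per patient; what is at stake is precision. If r is 0.3 to 0.7, adjustment is worth about 1 to 14 extra completers per arm (17.0 to 30.3 instead of 16). The CI half-width falls from 9.2 to between 8.9 and 6.7 points at SD 12.7, and from 13.0 to between 12.6 and 9.5 at SD 18. Below r of about 0.2 there is no gain and a small loss. These figures assume a two-sided 0.05 test and approximately normal scores with equal SDs in the two arms. This is an improvement that should be made, not a flaw that invalidates the trial.

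**What to change.** In III.F, before outcomes are seen:

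- Name one primary analysis: ANCOVA of 6-month VISA-P on arm and baseline VISA-P, one score per patient (with a rule for bilateral cases), patients analysed as randomised.
- Report the adjusted difference in VISA-P points with a 95% CI, and interpret it against 13 points.
- Keep Mann-Whitney, with a Hodges-Lehmann shift and CI, as a fixed sensitivity analysis, not one chosen by a normality check.
- As a supporting analysis, fit a mixed model over 1, 3 and 6 months with baseline as covariate (unstructured covariance, Kenward-Roger degrees of freedom, missing at random).
- Use the same baseline-adjusted ANCOVA for 6-month VAS-P ADL, VAS-P Sport and tendon thickness. The mixed model does not suit thickness, for which III.C specifies "Ultrasound measurements (performed at clinic visit at no additional cost) at baseline and 6 months"; confirm that the marks in the schedule table mean the same.

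**Cost.** The primary change takes a few sentences and one degree of freedom, and about 1.5 points of power if baseline and 6-month scores prove almost uncorrelated. The mixed model estimates more parameters, but only as support. No new data, visits or patients are needed.
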